## 10 Statistical methods and data analysis

By default [Section 10](#) and all the sub-sections below refer to the randomized section of the study: the same analysis timing, definitions and analysis conventions apply to the non-randomized section of the study, unless specified otherwise. Only arm 1A (spartalizumab + LAG525) will be analyzed in the non-randomized section of the study. In the non-randomized section of the study, the date of first dose of study treatment is used as reference date instead of the randomization date.

For the selection phase (part 1) and expansion phase (part 2), efficacy, safety, and biomarker analysis will be conducted on all subject data at the time that each part is completed. The primary analysis of each randomized and non-randomized section will be performed once the expanded arm has fully enrolled and also after all patients randomized/enrolled had at least 9 months of follow-up. This timing would allow for a potential minimum duration of response of 6 months for all subjects randomized/enrolled, assuming no delayed response. The exact timing of the primary analysis of the randomized section of the study could be revisited if more than one arm is expanded to part 2.

The additional data for any subjects continuing to receive study treatment past this time, as allowed by the protocol, will be further summarized in a final study report once these subjects complete the study.

Categorical data will be presented as contingency tables (frequencies and percentages). For continuous data summary statistics of mean, standard deviation, median, minimum, and maximum will be presented. For selected parameters, 25th and 75th percentiles will also be presented.

Screen failure subjects are those who signed the informed consent, but never started the study treatment for any reason. For these subjects, the eCRF data collected will not be included in analyses, but will be reported in CSR as separate listings.

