### 7.1.2.2 Information to be collected on screening failures

Subjects who sign the study ICF but are subsequently found to be ineligible prior to randomization/enrollment will be considered a screen failure. The demographic information, informed consent, and Inclusion/Exclusion pages must also be completed for screen failure subjects. No other data will be entered into the clinical database for subjects who are screen failures, unless the subject experienced a serious adverse event during the screening phase (see SAE section for reporting details). If the subject fails to be randomized/enrolled, the IRT must be notified within 2 days of the screen fail that the subject was not randomized/enrolled.

Subjects who are randomized/enrolled and fail to start study treatment for any reason will be considered an early terminator. The reason for early termination should be recorded on the appropriate Case Report Form.

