#### 10.1.1 Full Analysis Set

The Full Analysis Set (FAS) comprises all subjects to whom study treatment has been assigned by randomization. According to the intent to treat principle, subjects will be analyzed according to the treatment they have been assigned to during the randomization procedure regardless of whether or not treatment was administered. This population will be the primary population for efficacy analysis.

For non-randomized section of the study, the full analysis set (FAS) will be identical to the safety set.

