### 10.4.1 Variable

Objective response rate (ORR) is defined as the proportion of subjects with best overall response (BOR) of either confirmed complete response (CR) or confirmed partial response (PR), as per local review and according to RECIST v1.1 (see Appendix 2 for details).

[REDACTED]

ORR will be calculated based on the FAS. ORR and its 95% confidence interval will be presented by treatment group.

As a supportive analysis, ORR as per blinded independent central review (BICR) will be presented by treatment group; along with 95% confidence intervals (see [Section 10.4.4](#)).

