### **10.4.3 Handling of missing values/censoring/discontinuations**

For the computation of ORR, all confirmed responses (CR or PR) reported up to the analysis cut-off will be included. Subjects with no valid radiological assessment or unconfirmed responses will be considered as non-responders. Subjects who were non-responders before initiation of subsequent anti-cancer therapy will still be non-responders. In particular, subjects with CR or PR at the last radiological assessment prior to cut-off and no response at the previous assessment are by definition unconfirmed and will be considered as non-responders for the primary analysis.

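### Section 10's definition of screen failure, read literally, removes randomized but never-dosed subjects from analysis and so contradicts the intent-to-treat FAS used for ORR in the randomized section

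*Protocol*

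**What the plan says.** Two rules cover a subject who is randomized but never receives study treatment.

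- **Section 10, opening text.** "Screen failure subjects are those who signed the informed consent, but never started the study treatment for any reason". The next sentence reads: "For these subjects, the eCRF data collected will not be included in analyses, but will be reported in CSR as separate listings".
- **Section 10.1.1.** "The Full Analysis Set (FAS) comprises all subjects to whom study treatment has been assigned by randomization". Subjects are analysed in their assigned arm "regardless of whether or not treatment was administered", and this set is the primary efficacy population. For the non-randomized section the FAS is set equal to the safety set.
- **Section 10.4.1.** "ORR will be calculated based on the FAS".
- **Section 10.4.3.** "Subjects with no valid radiological assessment or unconfirmed responses will be considered as non-responders".
- **Section 7.1.2.2.** "Subjects who sign the study ICF but are subsequently found to be ineligible prior to randomization/enrollment will be considered a screen failure". By contrast: "Subjects who are randomized/enrolled and fail to start study treatment for any reason will be considered an early terminator".

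Section 6.1.1 and Table 7-1 allow up to 3 days between randomization and first dose, so such a subject can occur. Section 7.1.2.2 provides for one.

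**The concern.** The protocol defines screen failure in two ways and gives the same subject two fates. Under the opening text of Section 10, a randomized, never-dosed subject appears only in a listing. Under Sections 10.1.1, 10.4.1 and 10.4.3 that subject stays in the ORR denominator as a non-responder.

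The choice works in one direction only. A never-dosed subject counts as a non-responder, so removing one leaves ORR unchanged when there are no responders and raises it otherwise. The trial is open-label, and both the Part 1 decision rules and the final test depend on responders divided by subjects. The denominator should therefore not be open to choice.

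**Working it through.** **Step 1: the texts side by side, for a randomized subject who is never dosed**

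| Place | Status of the subject | In the ORR denominator? |
|---|---|---|
| Section 10, opening text | Screen failure | No, listing only |
| Section 10.1.1 with 10.4.1 | FAS member | Yes |
| Section 10.4.3 | Non-responder (no valid scan) | Yes |
| Section 7.1.2.2 | Early terminator | Not a screen failure |

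The first row conflicts with the other three. The protocol contains no precedence rule.

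**Step 2: reproduce the protocol's own figure**

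Section 10.4.2.1 rejects the null hypothesis (ORR at or below 10%) if the lower bound of the exact 95% CI exceeds 10%. The exact (Clopper-Pearson) lower bound for x responders in n subjects is the 2.5% quantile of Beta(x, n − x + 1).

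- 14/74: lower bound 10.75%, upper bound 29.7%. The protocol prints 10.8% and 29.7%; the difference is rounding.
- 13/74: lower bound 9.70%, not rejected. Table 10-2 prints 9.7%.

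The protocol's minimum of 14 responders in 74 is confirmed.

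**Step 3: remove k never-dosed subjects, keeping 13 responders** (k is assumed; the document does not give it)

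| k | x/n | Lower bound | Null hypothesis |
|---|---|---|---|
| 0 | 13/74 | 9.70% | not rejected |
| 1 | 13/73 | 9.84% | not rejected |
| 2 | 13/72 | 9.98% | not rejected |
| 3 | 13/71 | 10.13% | rejected |

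One or two exclusions change nothing; three reverse the conclusion. Treating N as fixed and ignoring Part 1 selection, take a true FAS ORR of 10%. The probability of 14 or more responders in 74 is 0.014. With three dropped, the response rate among the remaining 71 is 0.10 × 74/71 = 10.4%, and the probability of 13 or more is 0.031.

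**Step 4: the Part 1 rules**

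Section 10.4.2.1 uses the posterior Beta(y + 1, n − y + 1). An arm advances if P(ORR ≥ 20%) is at least 70% and is futile if P(ORR ≤ 15%) is at least 70%.

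- 3/13: P(ORR ≥ 20%) = 69.8%, no expansion. 3/12: 74.7%, expansion.
- 5/45: P(ORR ≤ 15%) = 70.7%, futile. 5/44: 68.6%, not futile.

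These sizes are realistic. Section 10.8.1 gives 13 subjects in arm 1 at the first interim, and 45 is the cap per arm. One subject can decide the outcome.

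**Step 5: what the document shows about actual counts**

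The Amendment 5 rationale gives 45, 43, 42 and 44 treated in arms 1 to 4. Section 4.1.1 gives 45 randomized in arm 1 and enrolment stopped at 44 in arm 4. Both match, so no randomized, undosed subject is visible in those two arms. Final randomized counts for arms 2 and 3 are not stated.

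**The case against.** The strongest reply is that the denominator is already fixed elsewhere, specifically and consistently. Section 10.1.1 names the intent-to-treat principle, Sections 10.4.1 and 10.5.2 apply the FAS to ORR, PFS and OS, and Section 10.4.3 counts unassessed subjects as non-responders. The glossary ties screen failure to unmet entry criteria. Against this stands one loosely worded introductory sentence that names no analysis set. A careful analyst would probably follow the FAS definition. That stands, and it limits the harm, but it does not remove the conflict: the exclusion is explicit, it opens the section that governs every analysis, and nothing subordinates it.

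A second reply also stands. The N=74 calculation belongs to an expansion of a randomized arm. All four randomized arms were declared futile, none was expanded, and none was enrolling at Amendment 5. The reversal also needs exactly 13 responders and at least three undosed subjects.

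A reader might infer that the two rules have already produced different results in the randomized arms. The document does not support that: arms 1 and 4 show no undosed subject, and for arms 2 and 3 it gives no final randomized counts. Nor would the exclusion make the estimate as-treated. Subjects would keep their assigned arm, so it would be a modified intent-to-treat estimate.

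**Conclusion.** The contradiction is real and confined to the randomized section. Read literally, the opening text of Section 10 drops randomized, never-dosed subjects, whom Sections 10.1.1, 10.4.1 and 10.4.3 keep as non-responders and Section 7.1.2.2 calls early terminators. The resulting ORR would be equal to or higher than the FAS ORR.

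The calculations show that the denominator can change a stated decision, not that it has done so. The numbers of undosed subjects (three in the N=74 example, one at an interim) are assumptions. The inference that arm 1A is at risk too does not hold for its ORR, because its FAS equals the safety set and untreated subjects are outside the denominator under either rule.

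The correction is still worth making. The final analysis described in Section 4.3 is still to come, and Section 4.1.1 allows further randomized arms to be added.

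**What to change.** Replace the definition in the opening text of Section 10 with: *Screen failures are subjects who signed informed consent but were not randomized (or, for arm 1A, not enrolled).* This agrees with Section 7.1.2.2, and the exclusion sentence that follows can then stand. Randomized, undosed subjects stay in the FAS as non-responders, as Sections 10.1.1 and 10.4.3 already provide, so no further rule is needed.

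The cost is one sentence, with no change to design, sample size or data collection.

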### 10.1 Analysis sets

All below defined analysis sets will be used to analyze data from both the selection phase (part 1) and the expansion phase (part 2).

[figure not shown]
#### 10.1.1 Full Analysis Set

The Full Analysis Set (FAS) comprises all subjects to whom study treatment has been assigned by randomization. According to the intent to treat principle, subjects will be analyzed according to the treatment they have been assigned to during the randomization procedure regardless of whether or not treatment was administered. This population will be the primary population for efficacy analysis.

For non-randomized section of the study, the full analysis set (FAS) will be identical to the safety set.

#### 10.1.2 Safety set

The Safety Set includes all subjects who received at least one dose of study treatment. Subjects will be analyzed according to the study treatment received, where treatment received is defined as the randomized treatment if the subject took at least one dose of that treatment or the first treatment received if the randomized treatment was never received.

[figure not shown]

**10.1.3 Per-Protocol set**

Not applicable.

**10.1.4 Dose-determining analysis set**

Not applicable.

## 10.1.6 Other analysis sets

### 10.1.6.1 Biomarker analysis set

The biomarker analysis set, as it pertains to the secondary objective (Section 10.5.5), consists of all subjects in the safety set with an evaluable baseline tumor biopsy sample and at least one evaluable post-baseline tumor biopsy sample. [REDACTED]

## 10.2 Subject demographics/other baseline characteristics

Demographic and other baseline data including disease characteristics will be listed and summarized descriptively by treatment group and for all subjects in the FAS and the Safety Set.

Categorical data will be presented as frequencies and percentages. For continuous data, mean, standard deviation, median, minimum, and maximum will be presented.

Relevant medical histories and current medical at baseline will be summarized separately by system organ class and preferred term, by treatment group and for all subjects.

## 10.3 Treatments (study treatment, concomitant therapies, compliance)

The Safety set will be used for the analyses below. Categorical data will be summarized as frequencies and percentages. For continuous data, mean, standard deviation, median, 25th and 75th percentiles, minimum, and maximum will be presented.

The duration of exposure in months to spartalizumab, LAG525, capmatinib, canakinumab and ribociclib as well as the dose intensity (computed as the ratio of actual cumulative dose received and actual duration of exposure) and the relative dose intensity (computed as the ratio of dose intensity and planned dose intensity) will be summarized by means of descriptive statistics using the safety set. The duration of exposure will also be presented for the study treatment by treatment group.

The number of subjects with dose adjustments (reductions, interruption, or permanent discontinuation) and the reasons will be summarized by treatment group and for all subjects, and all dosing data will be listed.

Concomitant medications and significant non-drug therapies prior to and after the start of the study treatment will be listed and summarized according to the Anatomical Therapeutic Chemical (ATC) classification system, by treatment group and for all subjects.

## 10.4 Primary objective

The primary objective of this study is to evaluate the preliminary efficacy (in part 1) and efficacy (in part 2) of spartalizumab in combination with novel agents in subjects with previously treated unresectable or metastatic melanoma.

### 10.4.1 Variable

Objective response rate (ORR) is defined as the proportion of subjects with best overall response (BOR) of either confirmed complete response (CR) or confirmed partial response (PR), as per local review and according to RECIST v1.1 (see Appendix 2 for details).

[REDACTED]

ORR will be calculated based on the FAS. ORR and its 95% confidence interval will be presented by treatment group.

As a supportive analysis, ORR as per blinded independent central review (BICR) will be presented by treatment group; along with 95% confidence intervals (see [Section 10.4.4](#)).

## 10.4.2 Statistical hypothesis, model, and method of analysis

### 10.4.2.1 Randomized section of the study

#### Part 1: Selection Phase

No formal hypothesis testing will be conducted in part 1. The objective of this part of the study is to explore the anti-tumor activity of the combination of spartalizumab with novel agents as measured by ORR per RECIST v1.1, and to select an arm(s) with promising efficacy that will be advanced to the expansion phase.

To determine whether arms have the potential to demonstrate clinically meaningful response rates, arms will need to show that they cross a specific efficacy probability threshold during the selection phase to advance to the expansion phase. Conversely, arms can also be shown to cross a specific futility probability threshold and consequently will be declared as futile and enrollment in those arms will be terminated. These thresholds and probabilities are highlighted in [Table 10-1](#).

**Table 10-1 Probabilities thresholds used to declare efficacy or futility for an arm**

Decision rule	Action
$P(\text{ORR} \leq 15\%) \geq 70\%$	Drop arm for futility
$P(\text{ORR} \geq 20\%) \geq 70\%$	Efficacy declared; Advance arm to expansion phase (part 2)

The futility decision rule was determined based on simulations such that arms with response rate that is not considered clinically meaningful (i.e.  $\text{ORR} < 10\%$ ) will be dropped with high probability (as illustrated in [Table 10-10](#) in [Section 10.8.1](#)). Similarly, the decision criterion for advancement to the expansion phase was determined so that arms with clinically meaningful response rate that warrants further development (i.e.  $\text{ORR} > 25\%$ ) will be advanced with high probability ('power') (see also [Table 10-10](#)).

To calculate these probabilities, a beta-binomial posterior distribution will be used as shown below:

$$p_i \sim \text{beta}(y_i + 1, n_i - y_i + 1)$$

where  $y_i$  are the number of confirmed responses in a combination arm (i), and  $n_i$  are the number of subjects enrolled in a combination arm (i). In calculation of the posterior distribution uninformed prior Beta[1,1] will be taken into account for each arm. The posterior probability will be calculated separately for each arm based on the observed ORR based on RECIST v1.1 criteria at each decision point, i.e. at each interim analysis as described in [Section 10.7.1](#).

No formal comparisons will be made between the combination arms for ORR in this 'selection' phase, instead each of the arms will be evaluated against efficacy and futility thresholds as presented above.

The final decision on whether an arm will be selected for advancement to the expansion phase will primarily be based on the observed ORR using decision rule described above but

other efficacy (in particular duration of response), safety, and biomarker data will be considered as well. Further considerations related to the design and execution of the selection phase will be captured in the SAP Technical Appendix.

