#### **2.4.1.1 Rationale for targeting subjects with LAG-3 positive melanoma in arm 1A**

The combination of LAG525 and spartalizumab has been explored in arm 1 within the CPDR001J2201 study in unselected metastatic melanoma patients who had progressed on prior anti-PD(L)-1 therapy, alone or in combination. Data from the first 35 patients enrolled in arm 1 were analyzed as part of the second interim analysis (IA2) and the safety profile of spartalizumab plus LAG525 (arm 1) was consistent with the safety profile of the individual drugs. The most common adverse events in arm 1 (>20%) were nausea (31.4%) and asthenia (22.9%). One subject reported multiple organ dysfunction syndrome as AE leading to treatment discontinuation and death. The main reason for treatment discontinuation was disease progression (57.1%). The ORR based on local radiology review per RECIST v1.1 was 8.6% (95% CI:1.8, 23.1) with 3 confirmed responders. The observed responses were durable with 2 responders ongoing for 7.4 months at the time of data cut off. The 3rd responder had brain metastasis and high LDH levels at enrollment and reported a duration of response of 3.7 months. LAG-3 status was determined for baseline tumor samples collected during screening using immunohistochemistry (IHC) analysis. Of the baseline biopsy samples from the 3 clinical responders, 2 samples were positive for LAG-3 and 1 sample was not evaluable for LAG-3 IHC evaluation but had high *LAG3* gene expression as analyzed by Nanostring. With only 4 of 35 patients total with positive LAG-3 tumor status, correlative analyses were limited in arm 1 hence further exploration is warranted to confirm these findings. Taken together, the preliminary data support further investigation to validate the hypothesis that the spartalizumab plus LAG525 combination could be effective in patients with positive LAG-3 tumor status. A centralized IHC assay will be used to select patients for arm 1A using a  $\geq 5\%$  threshold for positive LAG-3 staining in order to enroll the same patient population where an enrichment in response was observed in arm 1 during IA2.

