##### Part 2: Expansion phase

Arm 1A will be opened for enrollment in part 2 only if the pre-specified criterion defined in [Section 4.2.2](#) and [Section 10.4.2.2](#) for this arm is met.

Based on the sample size assumptions detailed in [Section 10.8.2](#), it is expected that up to approximately 80 subjects will be treated in arm 1A in the expansion phase, unless further exploration of this arm is stopped after 2nd interim analysis.

A second interim analysis will be conducted based on data from 20 additional subjects treated in expansion phase (i.e. 40 subjects in total combined with part 1 subjects) as described in [Section 10.4.2.2](#) to support and inform decision-making on whether the arm 1A will be further explored or dropped for futility.

Enrollment may be held after 20 subjects are treated in part 2 until the outcome of the 2nd interim analysis is available.

Novartis may decide at any time during the study to prematurely stop enrollment in arm 1A for any reason. The study design for the non-randomized section of the study is schematized in [Figure 4-2](#).

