**Table 10-4 Probabilities thresholds used to declare efficacy or futility for arm 1A**

Decision rule	Action
$P(\text{ORR} \geq 20\%) \leq 70\%$	Drop arm for futility
$P(\text{ORR} \geq 20\%) > 70\%$	Efficacy signal - Consider advancing arm to expansion phase (part 2)

The efficacy probabilistic threshold and decision criterion was determined so that a sufficient signal of efficacy needs to be observed before advancing this arm to the expansion phase and to ensure that if the true underlying ORR is 30% (clinically meaningful ORR) then the probability of crossing the threshold is sufficiently large (refer to [Table 10-12](#)).

To calculate the posterior probabilities, a beta-binomial posterior distribution will be used as shown below:

$$p \sim \text{beta}(y + 1, n - y + 1)$$

Where  $y$  is the number of confirmed responses in arm 1A and  $n$  is the number of subjects treated. In calculation of the posterior distribution, uninformed prior Beta[1,1] will be taken into account. The posterior probability will be calculated based on the observed ORR using RECIST v1.1 criteria at interim analysis as described in [Section 10.7.2](#).

The final decision on whether the arm will be selected for advancement to the expansion phase will primarily be based on the observed ORR using decision rule described above but other efficacy (in particular duration of response), safety, and biomarker data will be considered as well. Novartis may decide to not expand the arm despite the efficacy probability threshold crossed.

With 20 treated patients, 5 or more responders need to be observed to meet the efficacy probabilistic threshold as illustrated in [Table 10-5](#).

**Table 10-5 Posterior probability ORR≥20% given observed ORR at time of 1st interim analysis of selection phase**

# of Responders out of 20	ORR observed (%)	PP(ORR≥20%   observed ORR) (%)
0	0	0.9
1	5	5.8
2	10	17.9
3	15	37.0
4	20	58.6
5	25	76.9
6	30	89.1
7	35	95.7
8	40	98.9

# of Responders out of 20	ORR observed (%)	PP(ORR≥20%   observed ORR) (%)
9	45	99.6
10	50	99.9

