## **10.7 Interim analysis**

### **10.7.1 Randomized section of the study**

#### **Part 1: Selection phase**

As described in [Section 4.2.1](#), the first interim analysis is planned for ORR once at least ten subjects have been randomized into each of the three initial treatment groups (arm 1, arm 2, arm 3), and have either completed two post-baseline tumor assessments or have discontinued study treatment. Subsequent interim analyses will be conducted approximately every five months thereafter since that is the scheduled timeframe to have two post-baseline scans. The first interim analysis for arm 4 (ribociclib and spartalizumab) will be synchronized with the subsequent planned interim analyses for the other arms and will occur when at least 10 subjects have been randomized to that arm, and have either completed two post-baseline tumor assessments or have discontinued study treatment. Enrollment and assessment at subsequent interim analyses for each treatment group will continue until the criteria for futility or advancement into the expansion phase have been met, or 45 subjects have been randomized into a treatment group using decision rules presented in [Section 10.4.2.1](#).

Of note, interim analyses will continue to be performed in the randomized section of the study at the pre-defined frequency until a clinical decision (e.g. arm declared futile or efficacy probabilistic threshold crossed) on each arm in part 1 has been made. Even if declared futile, combination arms will be analyzed at subsequent interim analyses until all

subjects have been reported at least once (i.e. had a minimum follow-up of 20 weeks). Additional descriptive analyses may be performed if required.

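### Section 10.4.2.1 defines n in the interim posterior as all subjects enrolled, which contradicts the followed-subject denominators behind Table 10-10 and, read literally, pushes the randomized arms toward futility

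*Protocol*

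**What the plan says.** **Randomized arms.** Section 10.4.2.1 gives the posterior for arm i as Beta(y_i+1, n_i−y_i+1), where y_i counts confirmed responses and the n_i "are the number of subjects enrolled in a combination arm (i"). The prior is flat: "uninformed prior Beta[1,1] will be taken into account for each arm". Table 10-1 drops an arm if P(ORR≤15%) ≥ 70% and advances it if P(ORR≥20%) ≥ 70%.

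**Who counts as a failure.** Section 10.4.1 states "ORR will be calculated based on the FAS", which in this section means everyone randomized. Section 10.4.3 adds "Subjects with no valid radiological assessment or unconfirmed responses will be considered as non-responders".

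**When a look happens.** Section 10.7.1 waits for at least ten subjects per arm who "have either completed two post-baseline tumor assessments or have discontinued study treatment". Further looks follow about every five months, and enrolment continues until a criterion is met or 45 are randomized. This wording fixes the timing of a look. No sentence in Section 10 uses it to restrict n_i.

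**Denominators used elsewhere.**
- Section 10.8.1 simulates the first interim with 13, 10 and 12 subjects in arms 1 to 3.
- Section 2.4.1.1, on the second interim: "Data from the first 35 patients enrolled in arm 1 were analyzed", with 3 confirmed responders (8.6%). Section 4.1.1 says 45 were randomized to that arm.
- Sections 4.2.1 and 10.7.1 keep re-analyzing futile arms until every subject has been reported with at least 20 weeks of follow-up.

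**Arm 1A.** In Section 10.4.2.2, n "is the number of subjects treated". Section 4.2.2 holds the first look until all 20 are followed or have discontinued. Sections 4.1.2, 10.4.2.2 and 10.8.2 put the second look at 40 subjects, with 9 responders needed. The enrolment pause is optional: "Enrollment may be held after 20 subjects are treated in part 2 until the outcome of the" second interim analysis.

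**The concern.** The first scan is at week 12 and a response is confirmed no less than 4 weeks later (Section 7.2.1.2). A subject randomized less than about 16 weeks before the cut-off therefore cannot be a confirmed responder. If n_i is everyone enrolled, each such subject adds one to the denominator and nothing to the numerator. The posterior shifts downward, and the shift grows with accrual speed, not with anything the drug does.

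The rule as written is then not the rule whose error rates the protocol reports. Section 10.8.1 says an arm with true ORR 25% is declared efficacious with approximately 70–79% probability, and Section 10.4.2.1 relies on the same simulations for the chance of dropping a poor arm. A rule with two readings, at looks where one or two responders decide the outcome, also allows the denominator to be chosen after the data are seen.

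**Working it through.** **Inputs.** Thresholds and prior: Section 10.4.2.1. First-look sizes 13/10/12 and accrual of 8 per month: Section 10.8.1. First interim at about month 9: Section 10.8.1. Cap of 45: Section 10.7.1.

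**Step 1: reproduce Table 10-10 with n = followed subjects.** I used exact binomial enumeration with the Beta posterior at each look. Looks were at 13/33/45 (arm 1), 10/30/45 (arm 2) and 12/32/45 (arm 3). The second-look size is my assumption; a step of 20 per arm fitted best among 8, 10, 13, 16 and 20.

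| Arm | True ORR | Table 10-10, futile / efficacious (%) | Recomputed (%) |
|---|---|---|---|
| 1 | 10% | 75.35 / 4.57 | 75.1 / 4.3 |
| 1 | 25% | 4.82 / 71.07 | 4.6 / 72.0 |
| 2 | 10% | 75.55 / 8.63 | 77.2 / 8.3 |
| 2 | 25% | 7.45 / 73.91 | 8.5 / 75.3 |
| 3 | 10% | 72.91 / 11.53 | 73.2 / 11.5 |
| 3 | 25% | 5.40 / 78.86 | 5.4 / 77.3 |

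All agree within 2 points, so the table was built on followed subjects.

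**Step 2: single decisions under the two denominators.**
- 2 responders, P(ORR≤15%): Beta(3,12) for 2/13 gives 0.35 (continue); Beta(3,25) for 2/26 gives 0.79 (futile).
- 3 responders, P(ORR≥20%): Beta(4,10) for 3/12 gives 0.75 (efficacious); Beta(4,22) for 3/24 gives 0.23. At 3/24, P(ORR≤15%) is 0.53, so the arm continues: it loses the efficacy call but is not dropped.

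**Step 3: number enrolled at the first look.** 8 per month × 9 months = 72; 72 / 3 arms = 24 per arm. This is derived, not stated.

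**Step 4: P(futile at first look | ORR 25%).** With n = 10, 12 or 13, only 0 responders is futile (1/10, 1/12 and 1/13 give P(ORR≤15%) of 0.51, 0.60 and 0.64). With n = 24, two or fewer is futile (2/24 gives 0.75, 3/24 gives 0.53). Responses are assumed to come only from the followed subjects.

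| Arm (followed) | n = followed: 0.75^m | n = 24 enrolled: P(Bin(m, 0.25) ≤ 2) |
|---|---|---|
| 1 (m = 13) | 2.4% | 33.3% |
| 2 (m = 10) | 5.6% | 52.6% |
| 3 (m = 12) | 3.2% | 39.1% |

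Range for the assumed enrolment: 12.7–24.4% with 18 enrolled per arm, and 58.4–77.6% with 30.

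**Step 5: over all looks, ORR 25%, n = 24 and then the cap of 45.** Futile: 36.1%, 55.2% and 41.9% for arms 1 to 3. Efficacious: 48.0%, 35.7% and 44.4%.

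**Step 6: the reported second interim for arm 1.** P(ORR≤15%) is 0.81 with 3/35 and 0.93 with 3/45. Both exceed 0.70.

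**The case against.** The strongest reply is that the intended denominator can be read off the rest of the document. Section 10.4.2.1 ties the calculation to the interims of Section 10.7.1. The simulations use 13/10/12, the second interim used 35 of 45, and the 20-week reporting rule makes sense only if shorter-followed subjects are left out. Execution details are deferred to a SAP Technical Appendix that is not shown. All four randomized arms are already declared futile. This stands as evidence of intent and as a limit on consequence. It does not stand as a defence of the text: the formula's only definition of n_i says enrolled, and the FAS and non-responder rules support that literal reading.

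It is also fair that Step 4 credits later enrollees with no confirmed responses. Those between about 16 and 20 weeks could have some, so the literal figures are upper values for a given enrolment.

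Two stronger readings are tempting, and the documents do not support them.
- *Arm 1A loses power at its interims.* The first look has no gap. For the second, one could compute that passing both looks at ORR 30% falls from 73.5% to 62.0% with 45 treated, or 52.0% with 50. That requires the word treated to override the explicit 40 subjects and 9 responders in Sections 10.4.2.2 and 10.8.2, the hold not to be used, and an accrual rate the protocol does not give.
- *An arm was wrongly dropped.* The denominators reported are followed-subject ones, and arm 1 is futile under either.

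**Conclusion.** The definition of n_i in Section 10.4.2.1 is wrong as written. It contradicts the denominators in the protocol's own simulations and reported interim, and applied literally it does not deliver Table 10-10. At the first look the chance of declaring a 25% arm futile would be 33–53%, against 2–6% with followed subjects. The larger figures assume 24 enrolled per arm and no confirmed responses among later enrollees. The all-look figures also assume the second-look size.

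The reach is limited. The documents show no past decision that turned on this, and no randomized arm is enrolling. The wording matters for the stated rule and for any randomized arm later added under the master protocol. For arm 1A it is a matter of aligning one phrase with decision rules already fixed elsewhere.

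**What to change.** In Section 10.4.2.1, define both n_i and y_i on an interim analysis set: subjects randomized at least 20 weeks (two scheduled post-baseline assessments) before the cut-off, with later subjects excluded from numerator and denominator alike. A time-based set is preferable to reusing the trigger wording, which would admit recent enrollees only if they had stopped early. Count the minimum of ten per arm in Section 10.7.1 on the same set.

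In Section 10.4.2.2, state that n is the first 20 and then the first 40 subjects by date of first dose, whether or not enrolment is held.

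The cost is one sentence in each of Sections 10.4.2.1 and 10.4.2.2 and a matching phrase in 10.7.1. No extra data are needed, and Tables 10-5, 10-6, 10-10 and 10-12 need no recalculation on this account.
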